#### 7.1.2 Unexpected AE –

Any adverse event not listed in Section 7.4.3.

#### 7.1.3 Serious AE-

Any adverse drug experience occurring at any dose that results in any of the following outcomes:

- death;
- a life-threatening adverse drug experience;
- inpatient hospitalization, or prolongation of existing hospitalization (as defined below in this section):
- a persistent or significant disability/incapacity; or a congenital anomaly/birth defect.
- Important medical events that may not result in death, be life threatening, or require hospitalization may be considered a serious adverse drug experience when, based upon medical judgment, they may jeopardize the patient or subject and may require medical or surgical intervention to prevent one of the outcomes listed in this definition.

Hospitalization for expedited AE reporting purposes is defined as an inpatient hospital stay equal to or greater than 24 hours. Hospitalization is used as an indicator of the seriousness of the adverse event and should be reserved for situations where the adverse event truly fits this definition and not for hospitalizations associated with less serious events. For example, a hospital visit where a patient is admitted for observation or minor treatment (e.g. hydration) and released in less than 24 hours would not be considered serious. Furthermore, hospitalization for pharmacokinetic sampling is not an AE, and therefore is not to be reported either as a routine AE or in an expedited report.

Version Date: 07-31-17

## 7.1.4 Unanticipated problem -

An unanticipated problem is any event/experience that meets ALL 3 criteria below:

- Is unexpected in terms of nature, severity or frequency given the research procedures that are described in the protocol-related documents AND in the characteristics of the subject population being studied.
- Is related or possibly related to participation in research. This means that there
  is a reasonable possibility that the incident may have been caused by the
  procedures involved in the research study. (see section 7.2)
- The incident suggests that the research placed the subject or others at greater risk of harm than was previously known or recognized OR results in actual harm to the subject or others.

#### 7.1.5 Protocol Violation-

A protocol violation is defined as any change, deviation, or departure from the study design or procedures of a research project that is NOT approved by the institution's IRB prior to its initiation or implementation, OR deviation from standard operating procedures, Good Clinical Practices (GCPs), federal, state or local regulations. Protocol violations may or may not be under the control of the study team or UVa staff. These protocol violations may be major or minor violations.

7.1.6 Suspected Adverse Reaction (as defined in 21 CFR 312.32 (a))-

Any adverse event for which there is a reasonable possibility that the drug caused the adverse event.

#### 7.2 Attribution Assessment

7.2.1 Attribution – The determination of whether an adverse event is related to a medical treatment or procedure. The attribution groups are:

Definite – Applies to those adverse events which, the investigator feels are incontrovertibly related to the vaccine. An adverse event may be assigned an attribution of definitely related if or when (must have all of the following):

- It follows a reasonable temporal sequence from administration of the test drug.
- It could not be reasonably explained by the known characteristics of the subject's clinical state, environmental or toxic factors, or other modes of therapy administered to the subject.
- It disappears or decreases on cessation or reduction in dose with re-exposure to drug. (Note: This is not to be constructed as requiring re-exposure of the subject; however, the group of definitely related can only be used when a recurrence is observed.)
- It follows a known pattern of response to the test drug.

Probable – Applies to those adverse events for which, after careful consideration at the time they are evaluated, are felt with a high degree of certainty to be related to the test drug. An adverse event may be considered probably related if or when (must have three of the following):

• It follows a reasonable temporal sequence from administration

Version Date: 07-31-17

of the test drug.

- It could not be reasonably explained by the known characteristics of the subject's clinical state, environmental or toxic factors, or other modes of therapy administered to the subject.
- It disappears or decreases on cessation or reduction in dose.
  There are important exceptions when an adverse event does
  not disappear upon discontinuation of the drug, yet drugrelatedness clearly exists (e.g. bone marrow depression, fixed
  drug eruptions, tardive dyskinesia).
- It follows a known pattern of response to the test drug.

Possible – Applies to those adverse events for which, after careful consideration at the time they are evaluated, a connection with the test drug administration appears unlikely but cannot be ruled out with certainty. An adverse event may be considered possibly related if or when (must have two of the following):

- It follows a reasonable temporal sequence from administration of the test drug.
- It could not readily have been produced by the subject's clinical state, environmental or toxic factors, or other modes of therapy administered to the subject.
- It follows a known pattern of response to the test drug.

Unlikely – Applies to those adverse events for which, after careful consideration at the time they are evaluated, are judged to be unrelated to the test drug. An adverse event may be considered unlikely if or when (must have two of the following):

- It does not follow a reasonable temporal sequence from administration of the test drug.
- It could readily have been produced by the subject's clinical state, environmental or toxic factors, or other modes of therapy administered to the subject.
- It does not follow a known pattern of response to the test drug.
- It does not reappear or worsen when the drug is readministered.

Unrelated – Applies to those adverse events, which after careful consideration, are clearly and incontrovertibly due to extraneous causes (disease, environment, etc.).

#### 7.3 Data collection

Data will be collected using a centralized electronic case report form called **ON**-line **Clinical Oncology Research Environment = Oncore**.

### 7.4 Risks and Safety

#### 7.4.1 Adverse Event Descriptions and Grading Scales

The NCI Common Terminology Criteria for Adverse Events (CTCAE) version 4.03 will be used for the characterization and grading of adverse events (see Appendix 6).

Version Date: 07-31-17

# 7.4.2 Time Span for Reporting Adverse Events

Reporting of AEs will begin when the subject is administered the study drug or has a study related biopsy. Events occurring through 30 days after administration of the last vaccine, regardless of attribution, will be reported. AEs should be followed to resolution or stabilization. If an AE worsens and becomes an SAE, it should be reported as serious per the guidelines specified for SAE reporting.

AEs that are possibly, probably, or definitely related to the vaccine will be recorded until the subject completes treatment follow-up. If, during treatment follow-up, the subject receives additional treatment, subjects will be off treatment follow-up and will be followed yearly for disease progression and survival.

7.4.3 Agent-Specific Expected Adverse Events List: Any AE not on this list will be considered an unexpected AE.

Expected toxicities related to peptide vaccines. This list of expected AEs for the LPV7 vaccine is based on prior data from the UVA-Mel 44 clinical trial in which 41 participants in Arm A received a mixture of 12 Class I peptides plus a tetanus helper peptide in an emulsion with Montanide ISA-51 adjuvant. AEs are listed only if observed in  $\geq$  5% of treated participants.

Table 7: Summary Toxicity Data from UVA-Me44 Grade 2:

CTCAE Category	Description		
Investigations	Lymphocyte count decreased		
General disorders and administration site conditions	Fatigue		
General disorders and administration site conditions	Fever		
Skin and subcutaneous tissue disorders	Hyperhidrosis		
Skin and subcutaneous tissue disorders	Skin induration		
Skin and subcutaneous tissue disorders	Skin ulceration		
General disorders and administration site conditions	Injection site reaction		
Gastrointestinal Disorders	Nausea		
Metabolism and nutrition disorders	Hyperglycemia		
General disorders and administration site conditions	Flu-like symptoms		
Skin and subcutaneous disorders	Other: any rash		

\*NOTE: Hyperglycemia  $\geq$  Grade 3 is not an expected event. If a non-fasting hyperglycemia adverse event occurs at a level  $\geq$  Grade 3, a fasting serum glucose test will be ordered and the event will be re-graded appropriately. The fasting serum glucose measurement will be used for the purpose of determining reporting requirements.

Injection site reaction/induration was experienced at maximum grade 3 in 5% of patients in Arm A of Mel44. Ulceration was experienced as maximum grade 3 in 7% of patients in Arm A of Mel 44. By the rule above (observed in  $\geq$ 5% of treated patients), injection site reaction, induration, and ulceration would be expected at grade 3. Despite this and in the interest of the patients, we would consider grade 3 injection site reaction with significant ulceration of the skin ( $\geq$  2 cm) as a DLT (see section 7.8).

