conditions	Application site pruritus	25%
	Application site reaction	None
	Fatigue	9%
	Rigors/chills	16%
Musculoskeletal and connective tissue disorders	Arthralgia	16%
Wusculoskeletal and connective tissue disorders	Myalgia	6%
Nervous system disorders	Headache	19%
	Lethargy/fatigue	13%
Psychiatric disorders	Not specified	16%
Skin and subcutaneous tissue disorders	Not specified	13%

Mild and transient leukopenia and thrombocytopenia have also been reported with use of resiquimod, but these are expected only to be grade I toxicities.

Toxicities at sites of resiquimod application should be limited to grade 1, 2, or 3 (with ulceration  $\leq$  2 cm) dermatologic toxicities, and should be manageable either by continuation of resiquimod if the patient is tolerating the toxicities and if the toxicities are relatively stable, or they may be managed by holding vaccination for one to several days (up to 7 days without being a DLT).

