## Adverse events expected with polyICLC (Hiltonol)

The following expected toxicities for polyICLC are based on the data from 45 patients treated with 20 mcg/kg 3x/w eek. This would be about 1.4 mg per dose and 4.2 mg per week (much higher than we will use).

Table 9: Toxicity Data for PolyICLC

Category	Toxicity	Grade	Comment		
Nervous system disorders	Headache	Grade 2	1 of 22 (<5%)		
	Tremors	Grade 3	2 of 45 (4%) poss related		
Musculoskeletal and connective tissue disorders	Muscle weakness	Grade 2	1 of 45 (<2%) experienced at Grade 3		
Respiratory, thoracic and mediastinal disorders	Dyspnea	Grade 2	1 of 45 (<2%) experienced at Grade 3		
mediastinal disorders	Нурохіа	Grade 2	1 of 45 (<2%) experienced at Grade 3		
Metabolism and nutrition disorders	Hypernatremia	Grade 2	1 of 45 (<2%) experienced at Grade 3		
	Elevated transaminases (GPT)	Grade 3	4 of 45 (9%) 3 cases possibly related; one case probably related. Typically transient.		
Investigations	Elevated Alkaline phosphatase	Grade 3	7% of patients, in IB		
	Leukocytopenia	Grade 3	2 of 45 (<4%) in published work; 20% in IB		
	Thrombocytopenia	Grade 3	14% of patients in IB		
	Neutropenia	Grade 3	10% of patients in IB		
Blood/lymph disorders	Anemia	Grade 3	13-31% of patients in IB		
General disorders and	Vaccine site reaction	Grade 2	1 of 22 (<5%)		
administration site conditions	Fever	Grade 3	14% of patients in RCC trial		
administration site conditions	Chills	Grade 3	10% of patients in RCC trial		
	Fatigue	Grade 3	10% of patients in RCC trial		

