# 7.8 Adverse Event Stopping Guidelines

Based on results from previous vaccinations with 12-MP and tetanus peptide preparations, and with findings from use of resiquimod and polyICLC, significant toxicity is not anticipated. The study will be monitored continuously for treatment-related adverse events within each vaccine preparation by the sponsor. Data from the UVA- Mel44 vaccine trial (Arm A) (using 12-MP and tetanus peptide) indicate an 8% rate of treatment-related unexpected Grade 3 adverse events.

Version Date: 07-31-17

Adverse events will be described and coded based upon the NCI CTCAE v4.03.

A DLT is defined as any unexpected adverse event that is possibly, probably or definitely related and:

- ≥ Grade 3, with the exception of grade 3 injection site reaction with ulceration ≤ 2 cm
- ≥ Grade 1 ocular adverse events as defined under Section 7.5
- ≥ Grade 2 allergic/autoimmune reactions

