# 9.0 STATISTICAL CONSIDERATIONS

This is an open-label, Phase I/II study evaluating the safety and immunogenicity of a long peptide vaccine (LPV7) + TLR for resected stage IIB – IV melanoma. There are two parts to the study.

For Part 1, the trial was designed to find the range of optimal combination therapies, defined as combinations with high immunologic response and an acceptable level of toxicity. The primary outcomes included the frequency of treatment related dose limiting toxicities (DLTs) and frequency of immunologic response. For Part 2, the goal is to obtain preliminary safety and immunogenicity data on the optimal combination identified in Part 1 when administered in the same skin site for all 6 vaccines (same site vaccination).

For part 2, the vaccine regimen is selected based on available data from Part 1, in which the strongest immune responses were observed in participants enrolled on Arms E and G (Table 1A). Resiquimod is no longer available; so the regimen for Arm G is not currently feasible. Also, the total enrollment on Arm E is larger (15 vs 6) so that outcomes from Part 2 will be evaluable in a similar sample size as for Part 1, Arm E. This group will be called Study Arm E2.

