Within each ordering, the continual reassessment method (CRM) is fit, using the working model and the accumulated data. The second stage will accrue eligible participants in cohorts of one and use a CRM model fit to estimate DLT probabilities at each arm combination. For each order,  $m=1,\cdots,6$ , in Table 16, the DLT probabilities for each arm  $i = 1, \cdots, 7,$ modeled via combination are а one-parameter pow er  $Pr({\sf DLT} \ {\sf at\ combination}\ i) pprox p_{mi}^{\theta_m}$  , where the  $p_{mi}$  are the working model values for order mgiven in Table 16. After accrual of each participant into the trial, the parameter  $\theta_m$  is estimated for each ordering by maximum likelihood estimation where the likelihood is given by  $\prod_{i=1}^{7} \left(p_{mi}^{\theta_m}\right)^{y_i} \left(1 - p_{mi}^{\theta_m}\right)^{n_i - y_i}$  where  $y_i$ = the number of DLTs and  $n_i$ =the number of treated participants in arm combination i. The order with the largest likelihood is chosen and within this ordering, DLT probability estimates are updated for each combination. If there is a tie between the likelihood values of two or more orderings, then the selected order is randomly chosen from among the tied orderings. These DLT probabilities will be used to define a set of "acceptable" combinations, defined as any dose with estimated DLT probability less than or equal to 33%. This toxicity tolerance of 33% was chosen based on the expectedness of adverse events.

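### By-arm DLT rates are not like for like: ten terms are expected at Grade 3 for polyICLC only, so the same related event can be a DLT in Arms A, C and F but not in B, D, E and G

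*Combined protocol and SAP*

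**What the plan says.** Section 7.8 sets the toxicity outcome: "A DLT is defined as any unexpected adverse event that is possibly, probably or definitely related and" meets one of three grade criteria. The main one is "≥ Grade 3, with the exception of grade 3 injection site reaction with ulceration ≤ 2 cm"; the other two cover ocular and allergic/autoimmune events at lower grades.

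Expectedness is decided in Section 7.4.3, whose heading line reads "7.4.3 Agent-Specific Expected Adverse Events List: Any AE not on this list will be considered an unexpected AE". The section then gives separate tables for the peptide vaccine (Table 7, Grade 2), resiquimod (Table 8, Grade 2), polyICLC (Table 9, mixed grades) and skin biopsies (Table 10, Grade 2). Table 9 is introduced with "The following expected toxicities for polyICLC are based on the data from 45 patients treated with 20 mcg/kg" three times a week.

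Two other places point to 7.4.3 without naming an arm or agent. Section 7.1.2 defines an unexpected event as "Any adverse event not listed in" that section, and step D of 7.6.1 treats an event as expected if it is listed there. No passage says whether a participant is judged against the tables for the agents received or against the whole section.

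Section 9.2.2 models one DLT outcome across all seven Part 1 arms. It calls a combination acceptable if it is "defined as any dose with estimated DLT probability less than or equal to 33" percent. Section 9.7.1 tabulates DLTs by arm at the end of the study.

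**The concern.** A toxicity rate can be compared between arms only if the same event is counted the same way in each. Here the exclusion for expected events depends on the list used, and the lists sit at different grades. Read by agent received, adding polyICLC to a regimen removes a block of Grade 3 events from the DLT count by definition. The counted rate can then fall while the harm to participants stays the same or rises.

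The model-based step relies on the opposite direction: every assumed ordering makes combinations with more agents at least as toxic. At stake are the meaning of the by-arm DLT table, any statement that one adjuvant is better tolerated than another, and the claim that the polyICLC arms, including the recommended Arm E, have acceptable toxicity.

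**Working it through.** **1. The plan's own figures.** Table 21 is the upper boundary of a sequential probability ratio test with p0 = 5%, p1 = 30%, α = 5%, β = 20%: the smallest whole d at or above

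[ln((1−β)/α) + n·ln((1−p0)/(1−p1))] / [ln(p1/p0) + ln((1−p0)/(1−p1))].

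This gives 1.905 at n = 4 (stop at 2), 2.050 at n = 5 and 2.924 at n = 11 (stop at 3), and 3.069 at n = 12 and 3.943 at n = 18 (stop at 4). Every n from 2 to 18 matches. The exact 95% interval for Arm E's 1/16 DLTs is 0.2% to 30.2%, as stated in 9.6.2. The monitoring arithmetic is sound; the question is what is counted.

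**2. The formal tables side by side.** All arms receive the peptide vaccine. Resiquimod is in C, D, F and G. PolyICLC is in B, D, E, G and E2.

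| Term | Table 7 (peptide/IFA) | Table 8 (resiquimod) | Table 9 (polyICLC) |
|---|---|---|---|
| Fever | Grade 2 | not listed | Grade 3 |
| Fatigue | Grade 2 | Grade 2 | Grade 3 |
| Chills | not listed | Grade 2 | Grade 3 |
| Neutropenia, anemia, transaminases, alkaline phosphatase, tremor | not listed | not listed | Grade 3 |
| Thrombocytopenia, leukopenia | not listed | Grade 1 only, in the text below the table | Grade 3 |

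That makes ten terms at Grade 3 for polyICLC and none of them at Grade 3 for the other agents. The remarks in 7.4.3 on Grade 3 local skin reactions concern other terms.

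**3. Is expectedness tied to grade?** The text treats it so. Hyperglycemia is in the Grade 2 list, yet a note under Table 7 says it is not expected at Grade 3 or above. Section 1.2.7 expects ulceration and injection site reaction at Grade 2 and does not expect Grade 3 injection site reactions.

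**4. The two readings, both grade-specific.**
- *By agent received:* a related Grade 3 event on any of the ten terms is a DLT in A, C and F, and is not in B, D, E, G or E2.
- *Pooled:* the same event is a DLT in no arm. The arms then share one rule, but events in A, C and F are excused through an agent those participants never received.

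**5. Against the model.** In all six rows of Table 16 the Zone 1 values lie between 0.01 and 0.12, the Zone 2 values between 0.20 and 0.36, and G is 0.45. A is below E every time (0.01 v 0.28, 0.01 v 0.36, 0.05 v 0.20, 0.12 v 0.20, 0.05 v 0.36, 0.12 v 0.28). A power model with a positive exponent keeps that order, so no ordering can represent a counted rate lower in E than in A.

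**6. Illustration (assumed rates, by-agent reading).** Suppose participants in A and E have the same underlying risks: h on Table 9 terms and, independently, 5% on other qualifying terms. The counted rate in E is 5%. In A it is 1 − (1 − h)(0.95):
- h = 4%: 1 − 0.96 × 0.95 = 8.8%
- h = 10%: 1 − 0.90 × 0.95 = 14.5%
- h = 14%: 1 − 0.86 × 0.95 = 18.3%

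The gap is 0.95h, so identical harm yields a reversed order for any h above zero. The documents do not give h.

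**The case against.** **The size is assumed.** This stands. Table 9 reflects about 4.2 mg of polyICLC a week, which the protocol itself calls much higher than its own use. At 1 mg weekly the exposure is 1/4.2, about 24% of that; at 1 mg every three weeks it is about 8%. Section 7.8 cites 8% treatment-related unexpected Grade 3 events with a peptide/IFA vaccine in an earlier trial, so 14.5% for Arm A is high. If A's counted rate were 8%, an arm with the same harm but polyICLC would count somewhere between 0% and 8%, depending on the share falling on Table 9 terms. The direction holds; the amount is unknown.

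**Expectedness is a deliberate choice.** Section 9.2.2 ties the 33% limit to it. That explains excluding expected events but does not make arms with different exclusions comparable.

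**All adverse events are tabulated by arm anyway.** Section 9.7.1 does give frequency, proportion and severity. It does not call for a participant-level count of related Grade 3 or higher events regardless of expectedness, which is the arm-neutral figure needed.

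**Fever and fatigue are already in Table 7.** If terms counted whatever their grade, those two would be expected in every arm. The other eight are not named in Table 7, so A and E would still differ, and the hyperglycemia note speaks against that reading.

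**A stronger inference about Part 2.** A reader might infer that the pooled wording lets the resiquimod list hide Grade 3 or higher DLTs in Arm E2, which has no resiquimod (Section 9.0: "Resiquimod is no longer available; so the regimen for Arm G is not currently feasible"). The documents do not support this. Table 8 is set at Grade 2, so under the grade-specific rule a Grade 3 arthralgia or skin event is not made expected by it. Pooling Table 8 would at most move some related Grade 2 events from the 15-day to the 30-day entry class in Table 12.

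**Conclusion.** The concern holds for comparisons between arms. Under the by-agent reading, which the heading of 7.4.3 favours, related Grade 3 events on ten terms count as DLTs in three arms and not in the other four. By-arm DLT rates then do not measure the same harm, and adding polyICLC can lower the counted rate against Tables 15 and 16. The 14.5% v 5% example shows the mechanism under assumed, independent and equal underlying rates; it estimates nothing in this trial.

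Two limits apply. A reader might infer that Arm E was chosen because its DLTs were under-counted. Nothing shows this: Part 1 is complete, Section 9.0 explains the choice by immune response, resiquimod supply and enrolment, and no document reports a changed allocation. Also, E and E2 both contain polyICLC, so their DLT rates are defined alike under either reading, although both leave out related Grade 3 events listed in Table 9.

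Sections 7.1.2, 7.4.3, 7.6.1 D and 7.8 must be reconciled. Which clinical rule should apply is for the sponsor.

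**What to change.** 1. Reconcile 7.1.2, 7.4.3, 7.6.1 D and 7.8 so that they state whether the lists apply by agent received or as one pooled list, and whether a term is expected only at its listed grade. State which rule was used for the Part 1 counts.
2. In 9.7.1 and 9.7.3, report for each arm (A to G and E2), beside the DLT rate, the number and proportion of participants with any related Grade 3 or higher event regardless of expectedness, with confidence intervals.
3. Base any toxicity comparison between arms, and any statement that a polyICLC arm is acceptable, on both figures.
4. Optionally, refit the 9.2.2 model once on the arm-neutral count as a sensitivity analysis.

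Cost: a wording change and one extra table from adverse event data already collected, plus one model run if the refit is done. The downside is that polyICLC arms may look less favourable than on the DLT rate alone.
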